### **5.4.3 Supportive Care**

Subjects should receive full supportive care, including transfusions of blood and blood products, antibiotics, anti-emetics, etc., when appropriate. Subjects who require therapeutic anticoagulation with low molecular weight heparin (e.g., enoxaparin and tinzaparin) at study entry will be eligible for enrollment. In addition, subjects requiring therapeutic anticoagulation with these agents during study participation will be allowed to remain on study therapy.

### **5.5 Criteria for Taking a Participant Off Protocol Therapy**

Duration of therapy will depend on individual response, evidence of disease progression and tolerance. In the absence of treatment delays due to adverse event(s), treatment may continue until one of the following criteria applies:

- Disease progression
- Intercurrent illness that prevents further administration of treatment
- Unacceptable adverse event(s)
- Participant demonstrates an inability or unwillingness to comply with the oral medication regimen and/or documentation requirements
- Participant decides to withdraw from the protocol therapy
- Investigator determines a change of therapy would be in the best interest of the subject
- Female subject becomes pregnant
- General or specific changes in the participant's condition render the participant unacceptable for further treatment in the judgment of the treating investigator
- Study Termination

Participants will be removed from the protocol therapy when any of these criteria apply. The reason for removal from protocol therapy, and the date the participant was removed, must be documented in the case report form (CRF). Alternative care options will be discussed with the participant.

An ODC Treatment Ended/Off Study Form will be filled out when a participant is removed from protocol therapy. This form can be found on the DF/HCC website at <http://www.dfhcc.harvard.edu/research/clinical-research-support/document-library-forms-sops-etc/>.

In the event of unusual or life-threatening complications, treating investigators must immediately notify the Overall PI, [REDACTED]

## **5.6 Duration of Follow Up**

Subjects will be followed for safety for 90 days following the last dose of study treatment or until receipt of another anticancer therapy, whichever comes first. Subjects who have an ongoing study treatment-related AE upon study completion or at discontinuation from the study will be followed until the event has resolved to baseline grade, the event is assessed by the site investigator as stable, new anticancer treatment is initiated, the subject is lost to follow-up, the subject withdraws consent, or until it has been determined that study treatment or participation is not the cause of the AE.

After progression/treatment discontinuation, subjects will be followed for survival and receipt of next line therapies every 6 months until death or 2 years after treatment discontinuation Follow-up will be via phone calls and through review of medical records.

## **5.7 Criteria for Taking a Participant Off Study**

Participants will be removed from study when any of the following criteria apply:

- Lost to follow-up
- Withdrawal of consent for data submission
- Death

The reason for taking a participant off study, and the date the participant was removed, must be documented in the case report form (CRF).

For Decentralized Subject Registrations, the research team updates the relevant Off Treatment/Off Study information in OnCore.

## **5.8 Replacement**

A subject who discontinues study participation prematurely for any reason is defined as a “dropout” if the subject has already been assigned to treatment or administered at least one dose of the study drug. Subjects who have dropped out will not be replaced.

## **6. TOXICITIES AND DOSE DELAYS/DOSE MODIFICATIONS**

Measures will be taken to ensure the safety of subjects participating in this trial, including the use of stringent inclusion and exclusion criteria and close monitoring. Eligibility criteria were

selected to guard the safety of subjects in this trial. Safety will be evaluated in this study through the monitoring of all serious and non-serious AEs, defined and graded according to CTCAE v4. Subjects will be assessed for safety (including laboratory values). General safety assessments will include serial interval histories, physical examinations, and specific laboratory studies, including serum chemistries and blood counts all serious adverse events (SAEs) and protocol defined events of special interest will be reported in an expedited fashion. In addition, the site investigators will review and evaluate observed AEs on a regular basis.

The descriptions and grading scales found in the revised CTCAE v4 will be utilized for dose delays. A copy of the CTCAE v4 can be downloaded from the Cancer Therapy Evaluation Program (CTEP) website

[http://ctep.cancer.gov/protocolDevelopment/electronic\\_applications/ctc.htm](http://ctep.cancer.gov/protocolDevelopment/electronic_applications/ctc.htm).

### 6.1 TAK-228 Dose Modifications

TAK-228 administration should be withheld for treatment-related adverse events that are Grade 3 or higher, despite supportive treatment per standard clinical practice. If the event resolves to Grade 1 or Grade 2 for hyperglycemia or rash or to baseline values within 2 weeks of interrupting treatment, then the subject may resume study treatment at a dose reduced by 1 level (see Table below). If study drug administration is delayed for more than 4 weeks (28 consecutive days) due to non-resolving study drug-related grade 3 toxicity despite supportive treatment per standard clinical practice, or more than 3 dose reductions of study drug are required in a subject, then study drug treatment should be stopped, the subject discontinued from the study, and the EOT visit completed within 30 days ( $\pm 7$ ) after the last dose of study drug.

If study drug administration is delayed for more than 6 weeks (42 consecutive days) due to non-treatment related adverse events, then study drug treatment should be discontinued, and EOT visit completed within 30 days ( $\pm 7$  days) after the last dose of study drug

If study drug is delayed for either less than 4 weeks (28 consecutive days) due to non-resolving study drug-related grade 3 toxicity or less than 6 weeks (42 consecutive days) due to non-treatment related adverse events, subjects should skip the dosing cycles missed and when if treatment is resume, this should be at the next scheduled dosing cycle.

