### 6.3 Management of Clinical Events

#### 6.3.1 Management of Hyperglycemia

Guidance for TAK-228 dose management in the event of hyperglycemia is provided in the table below.

Table 5: Management of Hyperglycemia

Grade	Description	Treatment	TAK-228 Dose Modification
1	Fasting blood sugar > ULN–160 mg/dL	Continue close monitoring of blood sugars. Consider initiation of oral hypoglycemic agent and/or insulin if not well controlled on oral agent.	None.
2	Fasting blood sugar > 160–250 mg/dL	Initiate oral hypoglycemic agent and/or insulin if not well controlled on oral agent.	None.
≥3	Fasting blood sugar > 250 mg/dL	Initiate oral hypoglycemic agent and/or insulin.	Hold drugs until ≤ Grade 2. Resume TAK-228 based on timing of recovery: ≤ 1 week: resume at same dose and schedule; >1 but ≤2 weeks: reduce TAK-228 by 1 dose level >2 weeks: discontinue subject from study

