### 6.3.5 Management of Rash

Guidance for TAK-228 dose adjustment for the event of rash is provided in the table below

Table 9: Management of Rash

Grade	Description	Treatment	TAK-228 Dose Modification
≤ 2	Macules/papules covering ≤ 30% body surface area with or without symptoms	Consider treatment with topical steroid cream/ointment and/or oral anti-histamines or antibiotics.	None.
≥ 3	Macules/papules covering > 30% body surface area with or without symptoms	Consider treatment with topical steroid cream/ointment, oral antihistamines, oral antibiotics, and/or pulsed steroids.	Hold until ≤ Grade 2; Resume TAK-228 based on timing of recovery and severity of symptoms: ≤ 3 weeks: reduce dose by 1 dose level; > 3 weeks and severely symptomatic: stop TAK-228 and discontinue subject from the study.

Subjects who develop Grade 4 rash should permanently discontinue study treatment, unless they derive clinical benefit as determined by the site investigator, in which case they may be retreated at a reduced dose level after recover to ≤ Grade 1 severity. Grade 4 rash is defined as rash acneiform and/or papulopustular with papules and/or pustules covering any % body surface area, which may or may not be associated with symptoms of pruritus or tenderness, AND are associated with extensive superinfection requiring with intravenous (IV) antibiotics indicated; life threatening consequences (NCI CTCAE Version 4.03, effective date 14 June 2010).

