### 6.3.6 Management of Nausea and/or Vomiting

Guidance for TAK-228 dose adjustment for the event of nausea and/or vomiting is provided in the table below.

Table 10: Management of Nausea and/or Vomiting

Grade	Description	Treatment	TAK-228 Dose Modification
≤ 2	Loss of appetite with or without decreased oral intake; 1-5 episodes of vomiting within 24 hours	Maximize anti-emetic therapy; Consider IV fluid hydration.	None.
≥ 3	Inadequate oral intake; ≥ 6 episodes of vomiting within 24 hours	Maximize anti-emetic therapy; Initiate tube feeding, IVF, or TPN.	If experienced for ≤72 hours, hold TAK-228 until ≤ Grade 1, then resume TAK-228 without dose modification. If experienced for >72 hours despite optimal therapy, hold TAK-228 until ≤ Grade 1, then resume treatment with the dose of TAK-228 reduced by 1 level.

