### 6.3.8 Management of Aspartate Aminotransferase/Alanine Aminotransferase Elevations

Table 14: Management of Aspartate Aminotransferase/Alanine Aminotransferase Elevations

Grade	Description	Treatment	Dose Modification
1	>ULN to 3×ULN	None	None
2	Asymptomatic with levels 3 to 5×ULN; >3×ULN with the appearance of worsening fatigue, nausea, vomiting, right upper quadrant pain or tenderness, fever, rash, or eosinophilia.	
 
Closely monitor LFTs at least weekly or more frequently as indicated.
 
Assess subject for other causes of transaminitis (eg, past medical history, concomitant medications).
 
	None
3	>5 to 20×ULN; >5×ULN for >2 weeks	Same as for Grade 2.	Hold TAK-228 until ≤Grade 1; Restart TAK-228 at the same dose. Permanently discontinue study treatment if in combination with Grade 2 total bilirubin elevation when alternative causes cannot be identified (ie, Hy's Law);
4	>20×ULN	Same as for Grade 2.	Stop TAK-228 and discontinue subject from the study.

Table 14: Management of Aspartate Aminotransferase/Alanine Aminotransferase Elevations

Grade	Description	Treatment	Dose Modification
			Permanently discontinue study treatment if in combination with Grade 2 total bilirubin elevation when alternative causes cannot be identified (ie, Hy's Law).

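### Section 6.1 and Tables 5 and 14 give different restart doses for the same Grade 3 event, the hold limits in 6.1 and Tables 5 and 9 do not line up, and no text says which governs

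*Combined protocol and SAP*

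**What the plan says.** Section 6.1 opens with a general trigger: "TAK-228 administration should be withheld for treatment-related adverse events that are Grade 3 or higher". It adds the condition that the event persists in spite of standard supportive care. If the event falls to Grade 1 (Grade 2 is enough for hyperglycemia and rash) or "to baseline values within 2 weeks of interrupting treatment, then the subject may resume study treatment at a dose reduced by 1 level". The outer limit for drug-related Grade 3 toxicity that does not resolve begins "If study drug administration is delayed for more than 4 weeks (28 consecutive days", and treatment then stops. A later paragraph covers shorter delays. It has the subject pick up at the next scheduled cycle and names no dose.

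The event tables in Section 6.3 give their own rules:

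- **Table 5, hyperglycemia, Grade 3 or higher.** After recovery in a week or less, "resume at same dose and schedule; >1 but ≤2 weeks: reduce TAK-228 by 1 dose level". Beyond that, ">2 weeks: discontinue subject from study".
- **Table 14, AST/ALT, Grade 3.** After recovery to Grade 1 or lower, "Restart TAK-228 at the same dose". Apart from its Hy's Law provision, the row sets no limit on the hold.
- **Table 9, rash, Grade 3 or higher.** One level lower if recovery takes up to 3 weeks, then "> 3 weeks and severely symptomatic: stop TAK-228 and discontinue subject from the study".
- **Table 10, nausea or vomiting, Grade 3 or higher, lasting 72 hours or less.** Hold until Grade 1 or lower, "then resume TAK-228 without dose modification".

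Most of these tables are introduced as guidance. Section 6 does not say whether 6.1 or the table applies where they differ.

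**The concern.** Two sites can face the same Grade 3 event in similar subjects and give different doses, each following the protocol. A monitor checking drug administration would have no single rule to check against. This is first a matter of subject safety and consistent conduct in a multicenter trial.

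It also touches the analysis. Section 12.2.1 counts responses only until progression or the end of trial therapy. Response must be confirmed at 4 weeks or more (Table 17), imaging is every 8 weeks, and Section 5.8 does not replace dropouts. Where the texts differ on when to stop, the length of a subject's response window can depend on which text the site follows. Where they differ on dose, the activity and toxicity reported for a 30 mg weekly start would come from a mixture of dose-modification schemes.

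**Working it through.** The plan gives no figure to reproduce here. The check sets the texts side by side and uses Table 4 to turn dose levels into milligrams.

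**Inputs.** Table 4: starting level 30 mg weekly; level -1, 20 mg; level -2, 15 mg; level -3, 10 mg. One level down from the start is (30 - 20) / 30 = 33% lower.

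**Comparison.** The subject is on 30 mg, has a treatment-related Grade 3 event, and has at least one dose withheld. Days count from the interruption.

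| Event and recovery time | Section 6.1 | Event table | Result |
|---|---|---|---|
| Hyperglycemia, by day 7 | 20 mg | Table 5: 30 mg | Restart doses conflict |
| Hyperglycemia, days 8-14 | 20 mg | Table 5: 20 mg | Agree |
| Hyperglycemia, days 15-28 | No stop required; no restart dose given | Table 5: discontinue | Limits not aligned |
| AST/ALT, by day 14 | 20 mg | Table 14: 30 mg | Restart doses conflict |
| Rash, by day 14 | 20 mg | Table 9: 20 mg | Agree |
| Rash, days 15-21 | Outside the 2-week window; no restart dose given | Table 9: 20 mg | Limits not aligned |
| Rash, severely symptomatic, days 22-28 | No stop required | Table 9: stop | Limits not aligned |
| Vomiting of 72 hours or less | 20 mg, if the supportive-care condition is met | Table 10: 30 mg | Ambiguous |

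Three things follow.

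1. In two rows no single dose satisfies both texts: hyperglycemia recovering within a week, and AST/ALT elevation recovering within 2 weeks.
2. Section 6.1 has a gap of its own. It permits resumption after recovery within 2 weeks and requires a stop after 4. For recovery between those points it contemplates resumption but states no dose.
3. The conflict is not general. For Grade 3 hyperlipidemia (Table 7), oral mucositis (Table 8) and other non-hematologic toxicity (Table 13), the tables call for a dose reduction, as 6.1 does.

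**The case against.** The best defence is that 6.1 is a general rule and the tables supply event-specific detail, so the table governs. This is a reasonable reading. That 6.1 names hyperglycemia and rash does not rule it out: they may be named only to set Grade 2 as their recovery threshold, which Tables 5 and 9 share. But the protocol never says that the tables prevail, and calling most of them guidance does not help. A site that applies 6.1 literally to hyperglycemia is also following the protocol.

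Other parts of the defence stand and limit the point:

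- **Table 10.** A reader might infer a flat contradiction. Section 6.1 applies where events persist in spite of supportive care. Section 6.2 says holding is not mandatory for nausea and diarrhea before optimal supportive care has been given. Table 10 reduces the dose only when the event outlasts 72 hours on optimal therapy. These can be read together, so Table 10 needs clarifying and is not shown to conflict.
- **Stop times.** A reader might infer that Table 5 and 6.1 are incompatible on discontinuation. A 2-week limit for one event can sit inside a 4-week general ceiling, and stopping under Table 5 breaches nothing in 6.1. What remains is that the limits are not aligned and days 15-28 are undefined in 6.1.
- **Rash.** Both texts reduce by one level. Only the timing differs.
- **Frequency.** A reader might infer that these are the dose decisions sites will make most often, because Section 11.1 lists hyperglycemia, nausea and vomiting among the common events. That list covers all grades and gives no Grade 3 rate. Section 6.3.1 says most hyperglycemia was Grade 1 or 2 and has not been dose-limiting since early treatment became standard.
- **Weekly dosing.** An event that resolves between doses may lead to no withheld dose, and it is then unclear whether the 6.1 restart clause applies.

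**Conclusion.** The inconsistency is real and confined to identifiable rows. For hyperglycemia recovering within a week and for Grade 3 AST/ALT elevation recovering within 2 weeks, the protocol supports both 20 mg and 30 mg after a 30 mg start. Hold limits for hyperglycemia and rash do not match 6.1, which is silent on the restart dose between 2 and 4 weeks.

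This assumes that the event is treatment-related, that a dose was withheld, and that 6.1 applies to events that also have a table, which the text neither confirms nor excludes. The 33% difference lasts only until the next dose change.

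A reader might go further and infer that the response rate is compromised, since 5 responses among 38 is the threshold for further study and one response could decide the result. The documents do not support that step: nothing in them indicates how many subjects would be affected or whether any would lose a response. What can be said is that dose, time on treatment and the response window can depend on which text a site follows. That is reason enough to correct the wording.

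**What to change.** Reconcile Section 6.1 with Tables 5, 9 and 14 so that each event has one restart dose and one maximum hold, including for recovery between 2 and 4 weeks. Clarify how Table 10 relates to the supportive-care condition in 6.1 and to the nausea and diarrhea text in 6.2. Add one sentence to 6.1 stating which text governs if they differ. The sponsor and drug supplier decide which rule is correct; this review takes no position on any dose or stopping time.

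The cost is wording in one protocol amendment and a memo to sites. No extra visits, tests or subjects are needed.

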### 6.2 Dose Levels for Dose Reductions

**Table 4: Dose Modifications for Single-Agent TAK-228**

Dose Level	Dose Regimen	TAK-228 Capsules: Number and Strength
Starting Dose Level	30 mg QW	Six 5-mg capsules
-1	20 mg QW	Four 5-mg capsules
-2	15 mg QW	Three 5-mg capsule
-3	10 mg QW	Two 5-mg capsules

QW=once weekly.

It is not mandatory to hold treatment in the absence of optimal supportive care for toxicities of nausea and diarrhea. Optimal supportive care is defined as an anti-emetic regimen that employs a 5-HT3 antagonist. If nausea and diarrhea persist despite optimal supportive care, treatment should be held until the subject returns to baseline.

In the case that a patient experiences persistent grade 1 or 2 toxicity, treatment with TAK-228 may be withheld at the discretion of the treating investigator. Once toxicity resolves in the case of grade 1 toxicity or resolves or at least improves to grade 1 in the case of grade 2 toxicity, treatment with TAK-228 may be resumed at the current dose level. If persistent grade 1 or 2 toxicity recurs, treatment with TAK-228 can again be held withheld at the discretion of the treating investigator. Once toxicity resolves in the case of grade 1 toxicity or resolves or at least improves to grade 1 in the case of grade 2 toxicity, treatment with TAK-228 may be resumed but at a reduced dose by one level.

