#### Prevention/Prophylaxis

- Follow fasting serum glucose levels during clinic visits.
- Monitor home glucometer test results.
- Check HbA1c levels every 3 months during therapy.

- 
- Life-style modifications, as appropriate (balanced diet, limit alcohol consumption, increase physical activity).
  - Most episodes of Grade 1 and 2 hyperglycemia respond quickly to oral metformin.
  - Early initiation of therapy is recommended to prevent higher grade hyperglycemia.
  - Fasting blood glucose levels  $\geq 150$  mg/dL by glucometer should be followed by closer monitoring of serum glucose and possible intervention.
- 

Abbreviations: dL = deciliters; mg = milligrams; ULN = upper limit of normal.

On the basis of the clinical experience in TAK-228 trials, most episodes of hyperglycemia observed occurred within the first 60 days after initiation of treatment with TAK-228 and have been either Grade 1 or Grade 2, and have responded quickly to oral metformin. Hyperglycemia has not been dose-limiting since the institution of a standard regimen for early treatment of hyperglycemia.

All subjects developing hyperglycemia during the study should have their glucose closely monitored by study staff. The site investigator may choose to continue close monitoring of subjects who develop Grade 1 hyperglycemia (fasting glucose  $>ULN \leq 160$  mg/dL) or, alternatively, consider initiating treatment with an oral hypoglycemic agent, such as metformin. All subjects with  $\geq$ Grade 2 hyperglycemia (fasting glucose  $>160$  mg/dL) must be treated aggressively with oral hypoglycemic agents and/or insulin as clinically indicated. The site investigator should consult an endocrinologist, if needed, to aid in optimizing the subject's hyperglycemia treatment plan.

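### After some Grade 3 events, section 6.1 and Tables 5 and 14 give different restart doses, and Table 14 and its own note give different Hy's Law stops; no precedence is stated

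*Combined protocol and SAP*

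**What the plan says.** Section 6.1 sets a general rule. Drug is withheld for "treatment-related adverse events that are Grade 3 or higher, despite supportive treatment per standard clinical practice". The restart condition is "If the event resolves to Grade 1 or Grade 2 for hyperglycemia or rash or to baseline values within 2 weeks of interrupting treatment", and in that case "then the subject may resume study treatment at a dose reduced by 1 level". Treatment stops "If study drug administration is delayed for more than 4 weeks (28 consecutive days) due to non-resolving study drug-related grade 3 toxicity", or if "more than 3 dose reductions of study drug are required in a subject". For shorter delays, the last paragraph of 6.1 has the patient skip what was missed and resume at the next scheduled cycle. It gives no dose.

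Section 6.3 then gives a table for each type of event:

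- **Table 5, hyperglycemia of Grade 3 or higher.** Hold until Grade 2 or lower. The restart then depends on recovery time: "≤ 1 week: resume at same dose and schedule". Recovery in more than 1 and up to 2 weeks means one level lower, and beyond 2 weeks the patient is discontinued.
- **Table 14, Grade 3 AST/ALT.** Hold until Grade 1 or lower, then restart at the same dose. Stop permanently if Grade 2 bilirubin elevation accompanies it and no other cause can be found, which the row equates with Hy's Law.
- **Note under Table 14.** Patients who meet Hy's Law criteria must stop, whatever the attribution and whether or not another cause exists.

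No sentence in section 6 says whether 6.1 or the 6.3 tables prevail, or whether the note overrides the row above it.

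**The concern.** The only restart dose that 6.1 states for a related Grade 3 event recovered within 2 weeks is one level lower. Two tables state the same dose for events that meet that description. The trial allows sites outside the lead consortium (sections 4.3 and 13.3), so two sites could treat the same event differently, each with protocol text in support. Departures from the protocol must be reported (Appendix E, section 3.8.1), so a site following one text could be cited under the other.

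The Hy's Law wording is a separate matter of liver safety. A patient with Grade 3 transaminases, Grade 2 bilirubin and a plausible other cause may restart under Table 14's Grade 3 row, but must stop under the note directly below it.

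**Working it through.** The check is mainly a comparison of texts. The only arithmetic is the size of the dose step.

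**1. Grade 3 AST/ALT, treatment-related, recovered to Grade 1 or baseline within 2 weeks.**

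- 6.1: one level lower.
- Table 14: same dose.
- The qualifier in 6.1 about supportive treatment does not separate the two. For Grade 3, Table 14's treatment column asks only for closer liver-test monitoring and a search for other causes.

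The two rules give different doses for the same event.

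**2. Hyperglycemia of Grade 3 or higher, treatment-related, recovered to Grade 2 within 1 week.**

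- 6.1: one level lower. Hyperglycemia is named in the recovery condition, so 6.1 cannot be read as covering only events without a table.
- Table 5: same dose and schedule.
- Here the qualifier narrows the overlap to events that persist despite treatment. The overlap is not empty, because Table 5 already starts hypoglycemic therapy at Grade 2. A patient who reaches Grade 3 on that therapy falls under both rules.

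**3. Size of the dose difference.** The inputs are the dose levels in Table 4 (section 6.2), where the row "Starting Dose Level" is 30 mg weekly and the reductions are 20, 15 and 10 mg. Section 5.2 gives 4 doses per 28-day cycle. Cycle total = 4 × weekly dose; relative difference = (table dose − 6.1 dose) / table dose.

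| Dose at event | Tables 5 and 14 | Section 6.1 | Cycle totals | Difference |
|---|---|---|---|---|
| 30 mg | 30 mg | 20 mg | 4×30 = 120 vs 4×20 = 80 mg | (30−20)/30 = 33% |
| 20 mg | 20 mg | 15 mg | 4×20 = 80 vs 4×15 = 60 mg | (20−15)/20 = 25% |
| 15 mg | 15 mg | 10 mg | 4×15 = 60 vs 4×10 = 40 mg | (15−10)/15 = 33% |
| 10 mg | 10 mg | stop | fourth reduction, over the limit of 3 | – |

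The last row assumes that the patient came down one level at a time. Following 6.1 also uses one of the three permitted reductions at each event, and following the tables uses none.

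**4. Hy's Law.** Take Grade 3 AST/ALT with Grade 2 bilirubin and an identified other cause.

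- Table 14, Grade 3 row: the stop is not triggered, and the hold-then-restart instruction applies at the same dose.
- Note: stop.

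Because the row equates Hy's Law with the absence of another cause, a literal reader could say that this patient never meets the criteria. The note's reference to other causes would then have no content, so its evident intent is to stop this patient. Table 14's Grade 4 row carries the same condition, but it stops treatment anyway.

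**The case against.** The strongest reply is that a specific table naturally governs over a general rule, and that 6.1 says a patient may resume one level lower without saying that nothing else is allowed. That reading is reasonable, and the proposed fix adopts it. But the protocol does not state it. 6.1 names two events that have their own tables, and section 6.3.1 introduces Table 5 only as guidance. Nor do the tables share a same-dose convention: where Tables 6, 7, 8, 9 and 13 restart after Grade 3, they reduce the dose, as 6.1 does.

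On Hy's Law, the note is mandatory, stricter and placed directly under the table, and stopping satisfies both texts. A careful reader would stop. This limits the harm to someone who relies on the row alone, but the two conditions still differ in substance.

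A reader might infer more than the documents support:

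- **Table 10 as a further contradiction.** It resumes Grade 3 or higher nausea or vomiting unchanged if it lasts 72 hours or less, and reduces one level if it lasts longer despite optimal therapy. That largely follows 6.1's own supportive-care distinction, so the difference is one of wording. With weekly dosing, such a short event may end before the next dose.
- **Rash as a conflict.** For rash recovered within 3 weeks, Table 9 reduces by one level, as 6.1 does. It gives no instruction for rash beyond 3 weeks that is not severely symptomatic, and the 4-week stop in 6.1 can fill that gap. Both can be followed.
- **6.1 as silent on recovery between 2 and 4 weeks.** Its last paragraph covers these delays. Only the restart dose is unstated.
- **Many patients affected.** Section 6.3.1 says that most hyperglycemia episodes "have been either Grade 1 or Grade 2, and have responded quickly to oral metformin", where the conflicting rules do not apply. The documents give no frequency for the events that matter here.

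**Conclusion.** Section 6 contains two restart-dose conflicts. Grade 3 AST/ALT is the more direct one, and hyperglycemia is narrower because 6.1 is limited to events that persist despite treatment. Both assume a treatment-related event that recovers within 6.1's 2 weeks (for hyperglycemia, within Table 5's 1 week). The difference is one dose level: 25% to 33% of the weekly dose, or stopping against continuing at 10 mg. Section 6.3.8 also states the Hy's Law stop in two ways that differ when another cause is identified.

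The percentages restate the dose steps. They do not measure harm or the extent of divergence between sites, and the documents do not allow an estimate of either. A reader might also infer that the response result is compromised. The documents do not support that: the response definition (12.2.1), the sample size and the two-stage rule (12.3) do not depend on these instructions. The issue is patient safety and consistent dosing, and it is worth correcting because the rules as written disagree.

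**What to change.** 1. In Table 14, delete the condition that no other cause can be found from the Grade 3 row, so that the note below is the single Hy's Law rule. Delete it from the Grade 4 row for consistency only.
2. In 6.1, state that the 6.3 tables govern the restart dose and recovery window for the events they name, and that 6.1's 4-week limit on delay and its limit of three reductions still apply unless a table is stricter. Table 5's discontinuation after 2 weeks is an example of a stricter rule.

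If the sponsor wants the reduction in 6.1 to apply to AST/ALT or hyperglycemia, Tables 14 and 5 should be edited instead. What matters is that one rule stands. While 6.1 is open, it would help to state the restart dose for related events that recover between 2 and 4 weeks and have no table.

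The cost is a wording amendment and a memo to sites. On its plain reading, the note already requires every stop that the Hy's Law edit would make explicit. Neither change touches the statistical design.
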